using clear, concise language^{130,131} and will include a short quiz to assess participants' understanding of the potential risks (as suggested by NIMH).¹³² To protect participant privacy, we use a speech detection system that does not record raw audio on the device, but, instead, destructively processes the data in real-time to extract, classify, and store features that are useful to infer the presence of human speech but not enough to reconstruct conversation content. Similarly, to protect participant privacy, we do not record any content of calls or texts, only the times in which the calls and texts occurred. Notably, the study team has consented tens of thousands of participants in clinical populations by informing them of these data signals.

Exclusion of High-Risk Populations. The current study will exclude persons who will be at high risk, specifically those with: (1) active suicidality, (2) psychosis, and (3) bipolar disorder. Treatment referrals will be made to those persons (see Clinical Referrals below).

Clinical Expertise and Supervision. All clinical assessments will be carried out by a postdoctoral fellow with a Ph.D. in clinical or counseling psychology using phone calls. Note persons who receive their Ph.D.'s in clinical and counseling have received years of training in clinical assessment and accrued 500 hours of patient contact prior to a predoctoral clinical internship and 1,500 hours of clinical experience on a clinical internship prior to graduating, as mandated by the American Psychological Association. The postdoctoral fellow will be given additional standardized training and supervised by [name]. All clinical assessments will be digitally recorded allowing assessors to be closely supervised by the research team. The postdoctoral fellow will make every attempt to help make the participants feel comfortable when discussing sensitive material. Importantly, telephone interviews themselves are associated with decreased distress compared and has been recommended to conduct interviews around sensitive topics.¹³⁶ Building on their clinical training and expertise, the postdoctoral fellow will be trained to respond with empathy and care, to ask follow-up questions that are relevant to the participants' responses and background, and to allow the questions to proceed at a comfortable pace (i.e., allowing time for silence, thought, reflection, and processing of this information).¹³⁶

Availability of the Study Team. [name] will be available to discuss the study or any concerns about the study with participants if requested by the participant and/or postdoctoral fellow. [name] will be available in the event of a clinical emergency, and this availability will be clearly communicated orally and in writing to study participants. Participants will be given a letter from investigators with information such as how to reach the investigators in the event of a clinical emergency. Participants will be referred to a treatment resource or a higher level of care if needed (i.e., hospitalization). Participants will be referred to a higher level of care if there is evidence of (1) acute active suicidality with a plan and intent to take one's life within a delineated period of time (i.e. less than 1 year), (2) acute homicidally with a plan or intent to take another's life, or (3) likelihood that they could immediately cause severe bodily harm to themselves or others (see Clinical Referrals below).

Ability to Withdraw. Participants may be able to withdraw from the study due to a significantly deteriorating course (e.g., need for hospitalization) or if the PI or participant determines that staying in the study is not in the participant's best interest. All participants who withdraw will be provided referrals for treatment.

Quality Control of Online Screen Data. To exclude duplication and ensure validity, Qualtrics checks every IP address and uses unique and sophisticated digital fingerprinting technology that is continuously being improved. Qualtrics is committed to providing the highest quality data to their clients. Qualtrics will replace respondents who finish less than half of the median survey completion length. Qualtrics also provides clients the opportunity to review the results and contact the Qualtrics team to request responses that need to be replaced, should there be any quality issues.

Data Security. All data on phones, on the server, and in-transit (including data sent from the wearable device to the phone) will be encrypted using industry standards (based on a 2048-bit encryption key; only the server can decrypt the data; and the data are physically stored on Amazon S3 data center servers protected by armed guards). The data collection and server storage are both fully HIPAA compliant.

Clinical Referrals. All participants will be given the phone number for the National Suicide Prevention Hotline, which is funded by the Substance Abuse and Mental Health Services Administration (SAMHSA). The hotline is staffed 24/7 by licensed mental health providers and is available throughout the United States. For persons not in acute risk who need a referral to outpatient treatment, we will identify referral sources using the Anxiety and Depression Association of America (ADAA), the Association for Behavioral and Cognitive Therapies (ABCT), the American Psychiatric Association, and the American Psychological Association. Each of these organizations maintains an active registry of current psychologists and psychiatrists across the country, many of whom provide the ability to also specify persons specializing in treating MDD. Participants in acute psychiatric emergencies will be directed to travel to their nearest emergency room,

Plan to Report any Participants Experiencing Potential Crisis:

All incidents of participants experiencing potential crises where follow-up is required will be reported within a week via email to CPHS, including a description of the action taken.

c. Describe why all the risks to subjects are reasonable in relation to both anticipated benefits and the knowledge expected to be gained from the study:

3. Potential Benefits of the Proposed Research to Human Subjects and Others

There are several potential benefits of the proposed research. Participants may experience reductions in their anxiety and depressive symptoms, as well as decreased cravings and reduced opioid use behaviors. In addition, there are also some salient potential benefits to other persons with anxiety and depressive disorders and OUDs based on the results from this work. In particular, this work could foster the ability to deliver behavioral treatments with little cost to persons needing treatment.

4. Importance of the Knowledge to be Gained

The knowledge to be gained from the proposed project has substantial public health importance. Anxiety and depressive disorders are common, severely disabling, and costly conditions. Thus, the current proposal will fill a crucial gap in knowledge regarding whether technology-based interventions for anxiety and depressive disorders might be used to improve treatment among persons receiving medication treatment for OUDs.

7. Unexpected Events or Incidental Findings

Note: It may be important to consider the potential for certain unanticipated events to occur, for example:

- finding an anomaly in a MRI
- discovering child abuse
- causing distress in interviews of a sensitive nature

Describe potential events and provide a plan of action:

[name] will be available to discuss the study or any concerns about the study with participants if requested by the participant. [name] will be available in the event of a clinical emergency, and this availability will be clearly communicated orally and in writing to study participants. Participants will be provided information such as how to reach the investigators in the event of a clinical emergency. Participants will be referred to a treatment resource or a higher level of care if needed (i.e., hospitalization). Participants will be referred to a higher level of care if there is evidence of (1) acute active suicidality with a plan and intent to take one's life within a delineated period of time (i.e. less than 1 year), (2) acute homicidally with a plan or intent to take another's life, or (3) likelihood that they could immediately cause severe bodily harm to themselves or others (see Clinical Referrals below).

Ability to Withdraw. Participants may be able to withdraw from the study due to a significantly deteriorating course (e.g., need for hospitalization) or if the PI or participant determines that staying in the study is not in the participant's best interest. All participants who withdraw will be provided referrals for treatment.

Clinical Referrals. All participants will be given the phone number for the National Suicide Prevention Hotline, which is funded by the Substance Abuse and Mental Health Services Administration (SAMHSA). The hotline is staffed 24/7 by licensed mental health providers and is available throughout the United States. For persons not in acute risk who need a referral to outpatient treatment, we will identify referral sources using the Anxiety and Depression Association of America (ADAA), the Association for Behavioral and Cognitive Therapies (ABCT), the American Psychiatric Association, and the American Psychological Association. Each of these organizations maintains an active registry of current psychologists and psychiatrists across the country, many of whom provide the ability to also specify persons specializing in treating anxiety and depression.

8. Placebo Use or Inconsistency with Standard of Care

Does any part of this study involve the use of a placebo or procedures that are inconsistent with the standard of care?

No Yes

If Yes, explain how the use of placebo or non-standard of care therapy may affect risks for participants, addressing the following:

- The safety and efficacy of other available therapies
- The maximum total length of time a participant may receive placebo on study
- The greatest potential harm that may result from not receiving or delaying effective therapy
- Safeguards for the participants receiving placebo or non-standard of care therapy

n/a

9. Genetics

Does any part of the study involve genetic analysis of biological specimens?

No

Yes, the study is based on the premise that a link between a genotype or a biomarker and a specific disease or condition is clinically useful in predicting the development of that specific disease or condition.

Please complete the [Genetic Research Form](#) and upload it to the 'Supporting Documents' page in Rapport.

-OR -

Yes, the study is looking for an association between a genotype or a biomarker and a specific disease or condition, but at this point it is not clear if the genetic marker has predictive value. The uncertainty regarding the predictive value of the genetic marker is such that studies in this category will not involve referral of participants to genetic counseling; however, participants will be informed of genetic testing in the consent form. **Please comment:**

We ask participants to take urine samples throughout the course of the study. We will send participants urine tests to their physical address. Then we will ask participants to take pictures of the urine tests and send them to the research team. Participants will have access to their results, but the study team will not collect any physical bio samples, just pictures of the urine test results.

10. Equitable Participant Selection

a. Estimated number of participants at Dartmouth CPHS reviewed sites:

The research team hopes to enroll 80 participants

b. Provide a justification of the proposed sample size

Participants will be recruited from an online study based on Google Adwords and Facebook advertisements as online recruitment has been shown to be a viable and cost-effective recruitment method for opioid users (Marshall et al., 2018).

c. Define the target population:

The participants will currently be receiving treatment for opioid use disorder. Additionally, participants must meet the following criteria: (a) Adults (age 18 or older), (b) fluent in English, (c) able to provide informed consent, (d) meet current criteria for OUD (as defined by a Rapid Opioid Dependence Screen), (e) are receiving methadone, buprenorphine, and/or naltrexone for OUD, and (f) meet current criteria for an anxiety and/or depressive disorder (based on the Patient Health Questionnaire and the Generalized Anxiety Disorder Questionnaire).

d. Vulnerable populations

Note: Certain populations are considered vulnerable to coercion and undue influence and are provided with additional protections when participating in a research study.

Identify any of the below populations which you plan to recruit for this study. In addition, complete the form(s) linked with each population as necessary and upload on the 'Supporting Documents' page in Rapport.

- [Pregnant Women, Fetuses and Neonates](#)
- [Children](#)
- [People with impaired decision-making capacity](#)

The following populations may also be considered vulnerable to coercion or other undue influence:

- Prisoners
- People who are economically disadvantaged
- The elderly
- People who are illiterate or do not speak English
- Students and employees

Describe any other potentially vulnerable population(s) and the additional protections provided to them:

We will not be recruiting vulnerable populations. All the participants will have the capacity to make informed consent.

11. Recruitment

Describe method(s) of recruitment. Associated advertisements and other materials to be used for recruitment should be uploaded to the ‘Consent Forms and Recruitment Materials’ page in Rapport.

The research team will recruit participants using Google Adwords and Reddit. Please see attached document for the advertisement that will be used. The add will contain a Qualtrics link that the participant can click on to access more information about the study and to sign up.

12. Informed Consent, Assent, and Authorization

All forms discussed in this section should be uploaded to the ‘Consent Forms and Recruitment Materials’ page in Rapport

a. Please describe the consent and/or assent process, addressing the following:

- Who will obtain consent/assent from participants
- Where the consent/assent process will take place
- The timeframe for providing information potential participants about a study, having the consent form signed, and beginning study activities
- Any precautions taken to minimize the possibility of coercion or undue influence
- The forms which will be used as well as any aids used to simplify scientific or technical information
- How comprehension will be ensured

Participants will be recruited online from Google Adwords and Reddit advertisements. If interested, participants will be prompted to click on the Qualtrics link for the consent form to fill out the screening questionnaires to see if they are eligible. Participants will be given screening questionnaires which include the Rapid Opioid Dependence Screening form and Opioid Craving Scale. Participants will also give permission to collect and keep contact information in this initial screening consent form. They will be prompted to give basic contact information such as name, telephone number, email address, and mailing address. If participants are eligible based on their answers to their responses to the screening questionnaires, they will receive the main consent form. Participants will receive an overview of the study containing the following information: (a) the nature of the study in its entirety, including both information about the questions asked during the screen,(b) data storage and retention plan, (c)who will have access to this information, and (d) research team contact information for any questions that the participant may have. Once participants have had all their questions answered and have read over the study summary and seen the info sheet, they will be prompted to sign the consent form electronically via Qualtrics link. All consent forms will be stored on a secure Dartmouth server that is password protected. Participants will also be able to access the Qualtrics link at all times and be able to scroll back and forth through the consent form.

b. Waiver(s) or alteration(s) may be requested for research that involves no more than minimal risk.

Indicate requested waiver(s) or alteration(s) below. In addition, complete the corresponding section of the [Waivers and Alterations Request Form](#) and upload it to the 'Consent Forms and Recruitment Materials' page in Rapport.

- For the informed consent *process*
- For the *documentation* of informed consent
- For the HIPAA Authorization to use and/or disclose PHI
- For a waiver of the requirement for medical record documentation

13. Financial impact on participants

a. List the tests, visits, and procedures performed for only research purposes and specify who will pay:

Note: Research procedures may not be billed to a health insurance plan

Participant Recruitment. A total of \$3,000 will be spent on online participant recruitment in the US only. We estimate a total cost of \$10 per participant to recruit 3000 participants, with an estimated enrollment of 2% of persons who complete the screen will enroll in the primary portion of the study.

Precision Dx 12-panel Urine Tests. The Precision Dx 12 Panel Cup test cups will cost a total of \$2,250.00 to purchase (we will need to purchase 300 units, with 25 units per case, we will need to purchase 12 cases with each case costing \$187.50). To save on shipping costs, the five tests will be mailed together to participants in one box. Participants will be asked to send a picture of the results label to save on shipping costs and so that no bodily fluids are traveling via mail. There will be an estimated \$720 in shipping costs.

Participant Remuneration: Participants will be paid \$15 for each pre, post, and follow-up questionnaire assessment and \$15 for each urine test (totaling \$120 per participant). Thus, the total cost requested for participant payment is \$7,200.

14. Compensation or Gifts

Please describe any payments, gifts or reimbursements participants will receive for taking part in the study:

Participants will be compensated via amazon giftcard for each component of the study they complete. They will receive 15 dollars for each questionnaire assessment they complete along with 15 dollars for each completed urine test. Compensation will be pro-rated if participants forget to complete any part of the study: The following information lays out the time points that participants will be compensated. Participants will not be compensated for completing the screening questionnaires.

Before the Digital Intervention: 30 dollars total

- 1) \$15 dollars for completing the self-assessment survey
- 2) \$15 dollars for providing the first urine (after 0 weeks) sample results.

After the Intervention is completed: 45 dollars total

- 1) 15 dollars for completing the post-intervention questionnaire
- 2) \$15 dollars for providing second urine sample (after 2 weeks)
- 3) \$15 dollars for providing third urine sample (after 4 weeks)

At the one-month follow-up: 45 dollars total

- 1) \$15 dollars for completing one-month follow-up post measures
- 2) \$15 for providing fourth urine sample results (after 6 weeks)
- 3) \$15 for providing fifth urine sample results (after 8 weeks)

15. Privacy of Participants

Note: Methods used to obtain information about participants may have an effect on privacy. For example:

- Consent discussions or interviews held in public which concern sensitive subjects or behaviors
- Observations of behavior, especially illicit behavior, in quasi-public settings

Describe any activities or interactions which could lead to a breach of privacy and provide a plan to protect participant privacy:

All Participants data will be collected and stored under a unique identifier. Any files linking the participant information and their study data will be stored on a password protected Dartmouth server. Participants' privacy will be safeguarded by fully informed consent by informing participants what data will be collected, who will have access to this information, and how knowledge of how information collected will be utilized and disseminated (Ziegeldorf, García-Morchón, & Wehrle, 2014).

16. Confidentiality of Data

Note: Any person engaged in research collecting information that could cause financial, social or legal harm to participants may apply for a [Certificate of Confidentiality](#). Certificates of Confidentiality are issued by the National Institutes of Health (NIH) to protect identifiable research information from forced disclosure. They are intended to allow the investigator and others who have access to research records to refuse to disclose identifying information on research participants in any civil, criminal, administrative, legislative, or other proceeding, whether at the federal, state, or local level.

a. If disclosed, could any of the data collected be considered sensitive, with the potential to damage financial standing, employability, insurability, or reputation?

No Yes

If Yes, describe the data or information, the rationale for their collection, and whether a Certificate of Confidentiality will be obtained:

Since we are collecting data about opioid addiction and urine test results, these results could potentially damage employability, reputation, and insurability. The research team believes that creating no-cost, scalable interventions for populations suffering from opioid addiction is an important step in advancing treatment for this population.

b. Describe the safeguards employed to secure, share, and maintain data during the study, addressing any of the following which may apply:

- Administrative, ie. coding of participant data
- Physical, ie. use of locked file cabinets
- Technical, ie. encrypted data systems

All data will be stored on a password protected Dartmouth server. We will use a two-document system. The coded identifier form will contain both the Study ID and any identifiable data from the participant. This data includes name, DOB, phone number, email, address and any other contact information collected during the study. This form will be destroyed at the end of the study. The second is the Data element form, which will contain any study information collected (pictures of the urine test results, assessments, and smart phone data)

c. Describe the plan for storage or destruction of data upon study completion:

Data will be preserved for the duration of the study. Once the study is completed the coded identifier form which is the document that connects the participant ID with their contact information will be destroyed. However, all data collected for the duration of the study will be kept indefinitely until it is no longer needed. All results will be stored on a password protected server which will only be accessed by study team members.

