1. Developing a novel technology-based intervention for anxiety and depressive symptoms among those receiving medication treatment for OUD.
2. Evaluating the feasibility of a technology-based intervention for anxiety and depressive symptoms among persons receiving treatment for OUD.
3. Evaluating the efficacy of a technology-based intervention for anxiety and depressive symptoms among persons with OUD.
4. Evaluating the efficacy of a technology-based intervention treating anxiety and depressive symptoms on cravings and opioid use among persons receiving medication treatment for OUD.

2. Objectives and Hypotheses

Aim 1: To test the feasibility and acceptability of the digital intervention designed to treat anxiety and depressive symptoms among persons receiving medication treatments for OUD.

Hypothesis 1: The digital intervention will show feasibility based on the ability to recruit participants (N = 40 within the digital intervention + medication treatment, N = 40 with medication treatment) and demonstrate acceptability of the application with greater than 50% of the intervention sessions completed on average by the treatment group.

Aim 2: To test the efficacy of a digital intervention targeting anxiety and depressive symptoms among persons receiving medication treatment for OUD. Sixty participants receiving medication treatment for OUD will be randomized to receive a digital intervention to treat anxiety and depression (N = 30) or care as usual (N = 30) for a total of four weeks.

Hypothesis 2: The digital intervention app group will experience (a) greater symptom reduction in anxiety and depressive symptoms (based on self-report measures) and (b) decreased opioid cravings and use across a four-week period (based on self-report measures and urine tests).

3. Study Design

Describe all study procedures, materials, and methods of data collection:

Recruitment. A population of 3000 adults who are receiving medication treatment for OUD will be recruited from an online study based on Google Adwords and Facebook advertisements as online recruitment has been shown to be a viable and cost-effective recruitment method for opioid users (Marshall et al., 2018).

We would also like to expand our recruitment efforts to Reddit sub-pages as well. Previous researchers looking at opioid addiction have had success posting in the Reddit forums and we would like to also recruit using this platform.

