Analyses. To test feasibility for **Hypothesis 1**, we will determine whether we can achieve the targeted enrollment ($N = 80$) and whether the average number of digital sessions is significantly higher than 50% based on multilevel binomial test nesting individual session completion rates within persons. To test **Hypothesis 2**, the current proposal will use intent-to-treat analyses employing multilevel modeling to examine moderation of change across time from pre to post, and post to follow-up. Based on power analyses, we will be well-powered to test the effects of the intervention (3-5 data points per person \times 80 participants = 180-300 \times 80% adherence = 144-240 data points total).

5. Study Progress Monitoring

Note: appropriate monitoring may include periodic assessment of the following:

- data quality
- timelines
- recruitment and enrollment

Provide a description of the methods which will be used to determine the progress of the study, including periodic assessments of data quality, timelines, recruitment, and enrollment as appropriate:

Recruitment. A population of 3000 adults who are receiving medication treatment for OUD will be recruited from an online study based on Google Adwords advertisements as online recruitment has been shown to be a viable and cost-effective recruitment method for opioid users (Marshall et al., 2018). We are only recruiting from the US.

We will also recruit via Reddit forum as well. Please see the document with the example of the post we would be planning on using.

Six opioid-focused subreddits were initially identified. Subreddits were selected based on their topical focus and their popularity. All were devoted to discussion of opioid use or recovery. In September 2019, the number of Redditors subscribed to each subreddit ranged from 4,000 to 82,000 people. Each subreddit was monitored by multiple moderators, who ensured all posts follow the Reddit community guidelines and remain focused on the topic of interest. All moderators in each of the six subreddits will be contacted by the study team to obtain approval to post the survey description and hyperlink. Moderators will be sent a study information sheet and a link to view the study description.

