, the study team believes that referring participants to helpful resources is sufficient given the nature of the study. We will not be actively monitoring suicidality throughout the study and will only ask the PHQ-9 at certain points during the study. If participants give concerning responses when questionnaires are administered there will be an automated referral process to initiate resources if persons indicate high suicidal ideation.

Additionally, there is evidence that administering questionnaires such as the PHQ-9 do not increase an individual's likelihood of suicidality. We do not believe that our study questionnaires will increase this likelihood. Again, anyone indicating suicidality in the screening questionnaires will not be eligible for the study. As we are mainly concerned with Opioid Use in our study demographic, we do not anticipate too many participants in our 80 person sample indicating high suicidal ideation, believe that our referral process will be sufficient.

b. Confirm that risks to subjects have been minimized, by use of procedures which are consistent with sound research design and which do not unnecessarily expose subjects to risk:

The study teams believes that they have taken the necessary precautions to ensure the safety of our participants.

Protection of Privacy. Participants' privacy will be safeguarded by fully informed consent by informing participants what data will be collected, who will have access to this information, and how knowledge of how information collected will be utilized and disseminated.¹²⁹ All participants must demonstrate comprehension (full understanding of study details), competence (ability to provide consent), and voluntariness (consent of their own volition) based on their phone calls with the postdoctoral fellow. Following suggestions for fully addressing privacy concerns in digital phenotyping studies, consent will be obtained through verbal discussion with a postdoctoral fellow

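### The same two-arm trial is sized at 80 in four places and at 60 in Aim 2, and the power statement's data-point count, the screening yield, the urine cups and the payments all work out to 60

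*Combined protocol and SAP*

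**What the plan says.** All references are to the combined protocol and SAP.

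**Places that give 80**
- Section 2, Hypothesis 1: "N = 40 within the digital intervention + medication treatment, N = 40 with medication treatment".
- Section 4, Analyses: for Hypothesis 1, "we will determine whether we can achieve the targeted enrollment", with N = 80 in brackets.
- Section 6, Risks & Benefits: "we do not anticipate too many participants in our 80 person sample indicating high suicidal ideation".
- Section 10a: "The research team hopes to enroll 80 participants".

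**Place that gives 60**
- Section 2, Aim 2: "Sixty participants receiving medication treatment for OUD will be randomized to receive a digital intervention to treat anxiety and depression (N = 30"), with another 30 in care as usual.

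**The power statement (section 4, Analyses)** multiplies 3-5 data points per person by the sample size and prints "80 participants = 180-300", then "80% adherence = 144-240 data points total".

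**The sample-size justification (section 10b)** describes only the recruitment channels: "Participants will be recruited from an online study based on Google Adwords and Facebook advertisements". It contains no calculation.

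**Resources (section 13)** are 3000 people screened with an estimated 2% enrolling, 300 urine cups in 12 cases of 25 at USD 187.50 a case, and USD 7,200 in payments at USD 120 per participant. Recruitment is budgeted at USD 3,000, alongside a unit cost of USD 10 for 3000 people.

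**The concern.** Section 3 describes one randomised two-arm trial, so it can have only one planned total. No passage calls the 60 a subset, a completer count or a later stage. A completer reading fails on two grounds: Aim 2 gives 60 as the number randomised, and 80% of 80 is 64.

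Two things depend on the answer. First, the sample size is itself a success criterion, because section 4 tests feasibility partly by whether 80 are enrolled. If recruitment goes as section 13 expects, the trial reaches the size Aim 2 sets and still misses the Hypothesis 1 target. Settling the target once enrolment is known would look post hoc. Second, the only assurance that the trial is well powered is the data-point line in section 4, and that line is false for the number of participants it names. The plan gives no effect size, significance level or power to fall back on.

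**Working it through.** **1. The plan's data-point figure (section 4).** Inputs: 3-5 points per person, 80% adherence, printed N of 80.

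| | N = 80 (as printed) | N = 60 | Plan states |
|---|---|---|---|
| 3 × N to 5 × N | 240-400 | 180-300 | 180-300 |
| × 0.8 | 192-320 | 144-240 | 144-240 |

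The stated figures do not reproduce at 80 and reproduce exactly at 60. Solving backwards: 180/3 = 300/5 = 144/(0.8 × 3) = 240/(0.8 × 5) = 60. If N is 80, the count is understated by 25% (180/240 = 300/400 = 0.75).

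**2. The other figures that imply a sample size**
- Screening (sections 3 and 13): 3000 × 0.02 = 60.
- Urine cups (section 13, with five tests per person in section 3): 300/5 = 60.
- Payments (section 13): 3 × 15 + 5 × 15 = USD 120 per person, and 7,200/120 = 60.
- Shipping does not discriminate: USD 720 is USD 12 a box at 60 and USD 9 a box at 80.

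**3. What 80 would require**
- Cups: 80 × 5 = 400, which is 16 cases at USD 187.50 = USD 3,000, against 300 cups and USD 2,250 (100 cups and USD 750 more).
- Payments at full completion: 80 × 120 = USD 9,600 against USD 7,200 (USD 2,400 more).
- Screening at 2%: 80/0.02 = 4,000 against 3000. The alternative is a yield of 80/3000 = 2.67%.

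**4. Chance of reaching 80.** Exact binomial, P(X ≥ 80). Only the 2% yield is the plan's; the higher yields are assumptions.

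| Screened | Yield | P(80 or more) |
|---|---|---|
| 3000 | 2% | 0.7% |
| 3000 | 2.25% | 7% |
| 3000 | 2.5% | 29% |
| 3000 | 3% | 87% |
| 4000 | 2% | 52% |

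**5. What the choice means for precision.** The plan gives no inputs, so this is an assumed illustration: two-sided 5% t test on two group means, no dropout, not the planned multilevel model. The detectable difference at 80% and 90% power is 0.74 and 0.85 SD with 30 per arm, and 0.63 and 0.73 SD with 40 per arm.

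**6. The recruitment cost line (section 13).** 10 × 3000 = USD 30,000, ten times the stated USD 3,000. At USD 10 each, USD 3,000 buys 300 screens, and 300 × 0.02 = 6 enrolled.

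**The case against.** The conflict itself is not in dispute; the arguments on the other side concern its consequences.

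- **The feasibility rule is clear.** Both places that state it say 80, and Aim 2's 60 is a design number under an efficacy aim. This stands in part. Read strictly, 60 enrolled misses the target. But the trial would then have failed on feasibility while recruiting exactly the number another part of the plan set out to randomise.
- **The data-point error is conservative.** At N = 80 the count is too low, and at N = 60 only the label is wrong. That is correct, and power is not overstated. The line still cannot support the claim it is offered for, and fixing N will not supply the missing effect size, significance level and power.
- **The screening route is fragile.** The 3000 is itself in doubt because of the cost mismatch, 2% is an estimate, and the Reddit recruitment has no stated yield. This stands. The probabilities above hold only if 3000 complete screening at the yield shown. Aim 2, the data-point product, the cups and the payments show the conflict without them.
- **The payment gap is a ceiling.** Section 14 pro-rates payment for missed components. If the 80% adherence in section 4 applied to every paid component (an assumption), 80 × 120 × 0.8 = USD 7,680, only USD 480 over budget. This is fair, but the plan's USD 7,200 is itself 60 × USD 120 at full completion, and on that basis the gap is USD 2,400. The cup gap stands in full, because all five tests are mailed together.
- **The four figures are not independent.** They may all descend from one earlier N of 60. True: they show that 60 was used in the calculations, not which N is intended now.

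**Conclusion.** The concern holds and must be fixed. The plan states two totals for one trial, and its text does not show which is intended. The printed 180-300 and 144-240 data points are wrong for 80 participants and right for 60. Expected enrolment on the plan's own screening figures is 60 against a feasibility target of 80. That is an expected shortfall of 20, not a certain failure, and it depends on 3000 completed screens, a 2% yield and no added contribution from Reddit. If 80 is intended, the cups are 100 short and the payment budget is USD 2,400 short at full completion. The factor-of-ten mismatch in recruitment cost is a separate error that neither choice of N repairs.

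**What to change.** Choose one N and use it in Hypothesis 1 and Aim 2 (section 2), the enrolment target and data-point line (section 4), the risk text (section 6), section 10a and the budget (section 13).

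**If 60:** restate every 80 as 60 and Hypothesis 1 as 30 + 30. The data-point, cup and payment totals then stand. The cost is text edits only, but the feasibility target and stated sample fall by 25%, and the plan gives nothing from which to judge whether 60 is enough.

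**If 80:**
- Correct Aim 2 to 40 + 40 and the data-point line to 240-400 (192-320 at 80% adherence).
- Raise cups to 400 (16 cases, USD 3,000; USD 750 more).
- Raise payments to USD 9,600 (USD 2,400 more at full completion).
- Raise screening to about 4,000 at 2%, or state the yield expected from Reddit. Screening 4,000 gives 80 only on average.
- Allow up to about USD 240 more for shipping, if USD 720 was set for 60 boxes at USD 12 (none if it was set for 80 at USD 9).
- Budget about 1,000 more screens: USD 1,000 if the USD 3,000 total is right, or USD 10,000 if the USD 10 unit cost is right.

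**In either case:** correct the recruitment line in section 13 so that unit cost times number screened equals the stated total.
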